7.3.2 Adverse Event Reporting to Country Regulatory Authorities by the Sponsor

The Sponsor will report SAEs to the country regulatory authority, per local requirements.

7.3.3 Complaints

The investigator is responsible for reporting all complaints to the Post Market Surveillance Department as they became aware of the complaint. A complaint is defined as any written, electronic or oral

Clinical Investigation Plan

communication that alleges deficiencies related to the identity, quality, durability, reliability, safety, effectiveness or performance of a device after it is released for distribution.

For Abbott/SJM products, the investigator must notify [REDACTED]

[REDACTED] as soon as possible after becoming aware of the complaint. For non-Abbott products, the investigator must notify the manufacturer of the device per that manufacturer's complaint reporting mechanisms or per the investigator's user facility procedures. This information is not collected on a CRF for the study.

8.0 STATISTICAL CONSIDERATIONS

The following section describes the statistical methods for the clinical study. The study will investigate the utility of electroanatomical mapping with HD mapping catheters and the EnSite Cardiac Mapping System as well as the outcome of subsequent RF ablation. The study is a prospective, multi-center, single-arm, unblinded observational study.

Endpoints described in Section 4.0 will be analyzed and reported using summary statistics. No hypothesis tests will be performed. Additional analysis using data collected in this study may be performed during or after completion of the 6-month and/or 12-month follow-up period for all subjects.

Nominal p-values may be presented to assess statistical significance using a significance level of 0.05. Statistical analysis will be performed using SAS version 9.3 or higher, or other analysis tools/software as necessary.

8.1 Analysis Populations

The analysis population used for all endpoints will include all subjects who have signed the Informed Consent Form and have undergone the electroanatomical mapping procedure using one of the specified HD mapping catheters and received RF ablation as specified in the protocol. If any device used during the procedure is used off-label, the subject will be excluded from non-safety related endpoint analysis and any additional evaluations.

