5.4 Subject Enrollment

A subject is considered enrolled in the clinical study from the moment the patient provides written informed consent, has been confirmed to meet all inclusion criteria and none of the exclusion criteria, and a HD mapping catheter (i.e. Inquiry™ AFocusII™ Double Loop or Advisor™ HD Grid Sensor Enabled™) inserted.

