7.3 Adverse Event Reporting

7.3.1 Adverse Event Reporting

Safety surveillance and reporting starts as soon as the patient is enrolled in the clinical investigation. Safety surveillance and reporting will continue until the last follow-up visit has been performed, the subject is deceased, the subject concludes participation in the clinical investigation or the subject

Clinical Investigation Plan

withdraws from the clinical investigation. Adverse event data, including deaths, will be collected throughout the time period defined above and will be reported to the Sponsor on a CRF. Additional information with regard to an adverse event should be updated within the appropriate CRF.

Unchanged, chronic, non-worsening or pre-existing conditions are not AEs and should not be reported.

An offline form will be made available to allow the investigator to report serious adverse events (SAEs) in the event the entry cannot be made in the EDC. This does not replace the EDC reporting system. All information must still be entered in the EDC system as soon as feasible.

Non-cardiac related abnormal laboratory values will not be considered AEs unless:

1. the investigator determined that the value is clinically significant,
2. the abnormal lab value required intervention, or
3. the abnormal lab value required subject withdrawal from the clinical investigation.

For the purposes of this clinical investigation, the following events will be reported:

- Adverse events that are considered related to either the ablation catheter or the ablation procedure by the investigator
- Adverse events resulting in death

Recurrence of AF, AFL, or AT are not considered reportable adverse events unless they occur in a severity, frequency, or other manner that is significantly worse than the subject's baseline condition. These are considered lack of effectiveness and will be reported as a recurrence on the appropriate case report form.

SAE Reporting

The investigator should report all SAEs to the Sponsor as soon as possible but no later than outlined below.

Clinical Site	Reporting timelines
All Sites	SAEs must be reported to the Sponsor no later than 3 calendar days from the day the site personnel became aware of the event or as per the investigative site's local requirements, if the requirement is more stringent than those outlined.

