8.2.2 Safety Endpoints Analysis

All pre-defined adverse events will be captured. Only adverse events that occur after the HD mapping catheter has been inserted (after enrollment) will be analyzed, as defined in the safety analysis population. Tables will be created that show cardiovascular serious adverse events.

[REDACTED]

[REDACTED]

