15.2 Risks Associated with Participation in this Clinical Investigation

Risks to subjects enrolled in this clinical study include those risks currently associated with other commercially available electrophysiology diagnostic procedures and RF catheter ablation procedures. The risks of the procedure are related primarily to mechanical injury to the heart and vessels from catheter manipulation and thermal injury due to RF current delivery, including the risk of thromboembolism and myocardial perforation, especially for ablations in the left atrium.

For those procedures where the physician applies sedation or anesthesia, the standard risks of anesthesia also exist and include allergic reactions, pneumonia, aspiration pneumonitis, atelectasis, prolonged sedation, other medical complications and in very rare cases, death.

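### Section 8.1 requires RF ablation for every endpoint analysis, so an enrolled subject whose procedure stops before RF drops out of the safety summary

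*Combined protocol and SAP*

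**What the plan says.** Section 8.1 describes a single set, introduced as "The analysis population used for all endpoints". Besides consent, a member must "have undergone the electroanatomical mapping procedure using one of the specified HD mapping catheters and received RF ablation as specified in the protocol". Its one safety exception concerns off-label device use: such subjects leave the non-safety endpoint analyses and the additional evaluations. Nothing is said about subjects who receive no RF.

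Other sections start from an earlier moment:

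- **5.4** completes enrolment when a consented patient satisfies every inclusion criterion and has, as the section puts it, "none of the exclusion criteria, and a HD mapping catheter (i.e. Inquiry™ AFocusII™ Double Loop or Advisor™ HD Grid Sensor Enabled™) inserted". RF is not part of the condition.
- **7.3.1**: "Safety surveillance and reporting starts as soon as the patient is enrolled in the clinical investigation".
- **8.2.2**, headed "Safety Endpoints Analysis": "Only adverse events that occur after the HD mapping catheter has been inserted (after enrollment) will be analyzed", followed by the words "as defined in the safety analysis population". Redacted blocks come next, and no readable section defines that population.

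Under 5.5 each enrolled subject stays in the study until follow-up is complete, and 11.4 requires CRF data for every enrolled subject.

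**The concern.** A subject can have the mapping catheter inserted, be enrolled and under surveillance, and never receive RF. The plan's own risk section makes this foreseeable. Section 15.2 says "The risks of the procedure are related primarily to mechanical injury to the heart and vessels from catheter manipulation" and names thermal injury from RF as a separate source of harm. A mapping complication that ends the procedure before RF is therefore possible, and in a study of mapping catheters it is a case the safety table should not lose.

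Under 8.1 that subject belongs to no endpoint analysis. An analyst who follows 8.1 and one who takes 8.2.2 to cover everyone from catheter insertion could report different complication rates from the same database. Omission biases the rate downward if complications are more frequent in subjects without RF than in the rest, and slightly upward if they are less frequent.

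**Working it through.** **Step 1: does 8.1 reach safety?** Yes, on three pieces of readable text. Section 8.2.2 calls the adverse event analysis an endpoint analysis in its heading. Section 8.0 treats what is described in Section 4.0 as endpoints, and 4.3, which lists adverse events, is part of Section 4.0. Section 8.1 itself speaks of non-safety endpoints, which implies that there are safety endpoints too.

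**Step 2: follow one subject through the plan** (catheter inserted, procedure stopped before RF).

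| Section | Status of this subject |
|---|---|
| 5.4 | Enrolled |
| 5.5, 11.4 | Stays in follow-up; CRF data required |
| 7.3.1 | Under safety surveillance |
| 8.2.2 | Events fall inside the analysed time window |
| 8.1 | Outside the population for all endpoints |

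**Step 3: size.** There is no figure in the plan to reproduce. The only input it supplies is N = 200, the approximate enrolment in 3.0. The other counts are assumptions:

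- c = enrolled subjects with a complication (8 or 4)
- n = enrolled subjects without RF (5 or 10)
- k = those among the n who had a complication (0, 1 or 2)

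All-enrolled rate = c/200. Rate under 8.1 = (c - k)/(200 - n). The 8.1 rate is lower only if k/n > c/200. Intervals are exact (Clopper-Pearson) 95%.

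All enrolled: 8/200 = 4.00% (1.74 to 7.73); 4/200 = 2.00% (0.55 to 5.04).

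| c | n | k | Rate under 8.1 (95% CI) | Change, points |
|---|---|---|---|---|
| 8 | 5 | 0 | 8/195 = 4.10% (1.79 to 7.92) | +0.10 |
| 8 | 5 | 1 | 7/195 = 3.59% (1.46 to 7.26) | -0.41 |
| 8 | 5 | 2 | 6/195 = 3.08% (1.14 to 6.58) | -0.92 |
| 8 | 10 | 0 | 8/190 = 4.21% (1.84 to 8.13) | +0.21 |
| 8 | 10 | 1 | 7/190 = 3.68% (1.49 to 7.44) | -0.32 |
| 8 | 10 | 2 | 6/190 = 3.16% (1.17 to 6.75) | -0.84 |
| 4 | 5 | 0 | 4/195 = 2.05% (0.56 to 5.17) | +0.05 |
| 4 | 5 | 1 | 3/195 = 1.54% (0.32 to 4.43) | -0.46 |
| 4 | 5 | 2 | 2/195 = 1.03% (0.12 to 3.66) | -0.97 |
| 4 | 10 | 0 | 4/190 = 2.11% (0.58 to 5.30) | +0.11 |
| 4 | 10 | 1 | 3/190 = 1.58% (0.33 to 4.54) | -0.42 |
| 4 | 10 | 2 | 2/190 = 1.05% (0.13 to 3.75) | -0.95 |

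One lost case puts the rate 0.32 to 0.46 points below the all-enrolled figure. The break-even for k = 1 is n = 200/c: 25 subjects without RF when c = 8 (7/175 = 4.00%), or 50 when c = 4 (3/150 = 2.00%).

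**Step 4: would such subjects occur?** The plan does not say. If 1% of procedures ended without RF (assumed), the chance of at least one among 200 is 1 - 0.99^200 = 0.87.

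**Step 5: a separate, smaller mismatch.** Section 4.3 promises all device-related events. The reportable list in 7.3.1 names deaths and events related to the ablation catheter or ablation procedure. Because 7.3.1 also asks for all SAEs, only non-serious mapping-catheter events are unclear. Section 6.2.3 places mapping before the ablation procedure, whereas 3.1 can be read as including it.

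**The case against.** The strongest reply is that 5.4, 7.3.1 and 8.2.2 say when the clock starts, not who is counted. An event window that opens at catheter insertion is compatible with an RF-treated population, since an ablated subject's mapping-phase events still count. On that view the dispute over membership rests on the reference to a safety population, and its definition may lie in the redacted text. A specific rule there would normally override the general sentence in 8.1. This is right about the window, and it is not claimed here that the definition is missing. But if the redacted definition includes subjects without RF, it contradicts the visible scope of 8.1; if it requires RF, it loses the cases at issue. Either way 8.1 needs new wording or a cross-reference.

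A second reply is that Section 4 gives the endpoint label only to 4.1 and 4.2 and places adverse events under additional evaluations. That reading is available, but it sits badly with the heading of 8.2.2, with 8.0 and with 8.1's own mention of non-safety endpoints. It also creates a difficulty in the off-label sentence, which removes subjects from additional evaluations and so, on that reading, from the adverse event analysis, unless the non-safety qualifier is taken to cover both items. The sentence can be read either way.

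Third, the RF requirement matches the acute and long-term success definitions in 4.2. That is correct, and those analyses need no change.

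Fourth, the only safety tables that the readable text specifies are of cardiovascular SAEs, so unreported non-serious mapping events would not alter them. This holds for those tables, but not for the wider promise in 4.3.

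Finally, all counts above except the 200 are assumed, the direction can reverse and the intervals overlap. That stands, and it limits how serious the point is.

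**Conclusion.** The concern holds. As written, 8.1 excludes from the safety summary a subject whom the rest of the plan enrols, monitors and follows. Over the assumed grid the complication rate moves by -0.97 to +0.21 percentage points. If no complication occurs in a subject without RF, there is no downward bias. If every enrolled subject receives RF, the two populations coincide.

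The effect is small against the sampling uncertainty, and with no hypothesis test and no pass/fail criterion (8.0, 8.10) no decision turns on it. The point should still be fixed, because the rule can remove mapping complications from the safety table of a mapping-catheter study. For events that 7.3.1 clearly makes reportable, the population can be corrected at analysis. Non-serious mapping events that sites never reported could not be recovered that way, so the clarification of 7.3.1 is the more time-sensitive part. Confidence is moderate, mainly because of the redacted text.

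**What to change.** In 8.1:

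1. Change the scope of the existing set to: *all endpoints and additional evaluations other than adverse events*. Keep the RF requirement for those analyses (utility, acute and long-term success, repeat ablation, EQ-5D-5L). Mapping time and mapping points can be measured without RF, so whether the utility endpoints need the condition is a separate choice for the sponsor to state.
2. Add: *Safety population: all enrolled subjects (HD mapping catheter inserted), regardless of RF delivery or off-label use*, to be used for the adverse events in 4.3 and 8.2.2. If redacted text already defines this set, refer to it in 8.1.
3. Reword the off-label sentence so that the exclusion covers *all endpoints and additional evaluations other than adverse events*.

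Report the number of enrolled subjects without RF, the reasons, and their adverse events. Separately, reconcile the reportable-event list in 7.3.1 with 4.3, so that sites know whether non-serious events related to the mapping catheter are covered.

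The cost is two wording changes and one added sentence in 8.1, plus a clarification in 7.3.1. No subjects or visits are added. The drawbacks are different denominators in safety and non-safety tables, which must be shown, possibly a few more non-serious reports, and a complication rate that may look slightly less favourable.

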8.2 Statistical Analysis

8.2.1 Characterization Endpoint Analysis

The endpoints will be summarized descriptively based on available data or measurements in the analysis population. No formal hypothesis testing will be performed.

In general, continuous variables will be summarized with the numbers of observations, means with standard deviations, minimums, and maximums as per the table mockups.

Categorical variables will be summarized with subject counts and percentages/rates, and where specified in the table mockups.

Survival analysis will be conducted to analyze time-to-event variables. Events occurring during the 90 days following the ablation procedure for AF subjects (90-day blanking period) will not be counted as an effectiveness outcome failure. Subjects without events will be censored at their last known event-free time

Clinical Investigation Plan

point. Subjects withdrawn or otherwise lost-to-follow-up during the follow-up period will be censored at their last known visit. Survival data will be presented using the Kaplan-Meier product limit method.

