4.3 Additional Evaluations

- Adverse events including any device-, procedure-, or death-related events.
- Rate of repeat ablations after study procedure during 12-month follow up defined as proportion of subjects with an additional ablation procedure to treat indicated cardiac arrhythmia (outside blanking period, if applicable).
- Change in quality of life (QOL) at 6 months and 12 months after receiving HD mapping and RF ablation relative to baseline: defined as change in quality of life assessed in the validated EQ-5D-5L QOL survey.

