5.5 Subject Withdrawal

Each enrolled subject shall remain in the clinical investigation until completion of the required follow-up period; however, a subject's participation in any clinical investigation is voluntary and the subject has the right to withdraw at any time without penalty or loss of benefit. Conceivable reasons for discontinuation may include, but not be limited to, the following:

- Subject death
- Subject voluntary withdrawal
- Subject lost-to follow-up as described below

The Sponsor must be notified of the reason(s) for subject discontinuation. The site will provide this information to the Sponsor. Investigators must also report this to their respective EC as defined by their institution's procedure(s).

No additional follow-up will be required or data recorded from subjects once withdrawn from the clinical investigation, except for the status (deceased/alive).

Lost-to-Follow-up

If the subject misses two consecutive scheduled follow-up time points and the attempts at contacting the subject detailed below are unsuccessful, then the subject is considered lost-to-follow-up. Site personnel shall make all reasonable efforts to locate and communicate with the subject (and document these efforts in the source documents), including the following, at each contact time point:

- A minimum of two telephone calls on different days over the specified follow-up windows to contact the subject should be recorded in the source documentation, including date, time and initials of site personnel trying to make contact.
- If these attempts are unsuccessful, a letter (certified if applicable) should be sent to the subject.
- If a subject misses one or more non-consecutive follow-up contact time points, it will be considered a missed visit. The subject may then return for subsequent visits. If the subject misses two consecutive time points and the above-mentioned attempts at communicating with the subject are unsuccessful, the subject will be considered lost-to-follow-up.

Clinical Investigation Plan

Note: Telephone contact with General Practitioner, non-clinical investigation cardiologist or relative without the presence of the subject or indirect documentation obtained via discharge letters will not be considered as subject contact.

[REDACTED]

[REDACTED]

[REDACTED]

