6.4.2 Patient Reported Outcomes

The Site Coordinator or designee will administer the EQ-5D-5L questionnaire at both the 6-month and the 12-month visit. It is important the subject understands the meaning of all words and instructions in the questionnaire. The subject should be instructed to ask any questions about the questionnaire if further explanation is needed. Once the questionnaire has been completed, the Site Coordinator or designee will review for completeness to verify that all questions have been answered according to the directions provided.

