8.7 Procedures for Accounting for Missing Data

Every effort will be made to collect all required data. All data available for the endpoints specified among the analysis population will be used. Missing data will not be imputed. Kaplan-Meier analysis will censor subjects withdrawn or otherwise lost-to-follow-up at last known visit.

[REDACTED]

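### Available-case means of EQ-5D-5L change at months 6 and 12 can rest on different (overlapping) subjects, and the month-12 mean is too high if poor month-6 responders tend not to return; add a repeated-measures estimate with its assumption stated

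*Combined protocol and SAP*

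**What the plan says.** Section 4.3 lists the evaluation: "Change in quality of life (QOL) at 6 months and 12 months after receiving HD mapping and RF ablation relative to baseline", measured with the EQ-5D-5L. The questionnaire is given at baseline (section 6.1.2), and section 6.4.2 adds: "The Site Coordinator or designee will administer the EQ-5D-5L questionnaire at both the 6-month and the 12-month visit".

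Section 8.0 sets the type of analysis: "Endpoints described in Section 4.0 will be analyzed and reported using summary statistics". Section 4.3 belongs to Section 4.0, so this covers quality of life. Section 8.2.1 says "The endpoints will be summarized descriptively based on available data or measurements in the analysis population" and, as a general rule, "continuous variables will be summarized with the numbers of observations, means with standard deviations, minimums, and maximums as per the table mockups". Section 8.7 says "All data available for the endpoints specified among the analysis population will be used. Missing data will not be imputed". The censoring rule in sections 8.2.1 and 8.7 concerns only the Kaplan-Meier analysis.

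On attendance, section 5.5 treats a single absence as a missed visit and adds: "The subject may then return for subsequent visits". Once a subject withdraws, only vital status is recorded.

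The visible text contains no repeated-measures estimate, no summary restricted to subjects with both visits, and no missing-data sensitivity analysis for EQ-5D-5L. Parts of section 8 are redacted and the table mockups are not shown, so this describes the visible text only.

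**The concern.** EQ-5D-5L is measured three times in the same subjects, but the plan summarises each visit on its own. This has two consequences.

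First, the sets of subjects behind the month-6 and month-12 means need not be the same. A reader who sets the two means side by side will read their difference as change over time, although part of it may be a change in who attended.

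Secondly, a subject seen at month 6 but not at month 12 drops out of the month-12 mean, although the month-6 score is in hand and says something about the missing value. If such subjects are mainly those with a poor month-6 response, the month-12 mean is too high, and a flat course can look like continued improvement.

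The study's aim is to quantify and characterise outcomes without formal testing, so the estimates themselves are its product. Section 8.0 also allows nominal p-values, which would carry the same bias.

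**Working it through.** **Inputs from the documents.** About 200 subjects (section 3.0); EQ-5D-5L at baseline, month 6 and month 12; available data, no imputation. The documents give no EQ-5D-5L SD, expected change, correlation or dropout rate, so there is no stated figure to reproduce.

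**Assumptions (not from the documents).** True mean change 0.05 at both visits; SD of change 0.18; correlation ρ between the month-6 and month-12 changes 0.5-0.7; proportion p missing at month 12 of 11-24%, with month 6 complete; odds of missing month 12 multiplied by OR = 1.6 to 2.7 per SD of poorer change.

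**Step 1: missingness follows the observed month-6 change.** Let z be the standardised month-6 change and π(z) = 1/(1 + exp(−(a − ln(OR)·z))) the probability of missing month 12, with a chosen so that the average of π is p. The mean of z among attenders is m = ∫ z φ(z)(1 − π(z)) dz / (1 − p). The error in the available-case month-12 mean is ρ × 0.18 × m.

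| p | OR | a | m | error, ρ = 0.5 | error, ρ = 0.7 |
|---|---|---|---|---|---|
| 0.11 | 1.6 | −2.175 | 0.0506 | 0.0046 | 0.0064 |
| 0.11 | 2.7 | −2.442 | 0.0987 | 0.0089 | 0.0124 |
| 0.24 | 1.6 | −1.208 | 0.1085 | 0.0098 | 0.0137 |
| 0.24 | 2.7 | −1.376 | 0.2042 | 0.0184 | 0.0257 |

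The corners are 0.5 × 0.18 × 0.0506 = 0.0046 and 0.7 × 0.18 × 0.2042 = 0.0257. The range is therefore about 0.005-0.026, or 10% to about 50% of the assumed change of 0.05.

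**Step 2: the likelihood estimate on the same data.** I simulated scores with SD 0.18 and baseline-to-follow-up correlation 0.5. This gives an SD of change of 0.18 × √(2 × (1 − 0.5)) = 0.18, and makes ρ equal to the correlation between the month-6 and month-12 scores. With baseline, month 6 and month 12 all as responses, the error in the month-12 mean change was below 0.001 in every row of the table. At n = 200 the standard error was 0.013-0.014 for either method. The available-case error is thus about 0.005/0.013 = 0.4 to 0.026/0.014 = 1.9 standard errors.

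**Step 3: missingness follows the unrecorded month-12 change.** The available-case error becomes 0.18 × m, that is 0.18 × 0.0506 = 0.009 to 0.18 × 0.2042 = 0.037. The share left in a likelihood estimate is approximately the part of the month-12 change that earlier data do not explain. From the month-6 change alone this is 1 − ρ²: 1 − 0.25 = 0.75 at ρ = 0.5, and 1 − 0.49 = 0.51 at ρ = 0.7. With baseline also in the response vector, the simulated share was 0.67-0.69 and 0.49-0.51 respectively. About half to three quarters of the bias therefore remains.

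**Step 4: missing completely at random.** Neither method is biased.

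**Step 5: subjects with both visits.** Restricting to them makes the two means comparable in composition but does not correct the selection. In the Step 1 scenarios their month-6 mean is raised by 0.18 × m and their month-12 mean by only ρ × 0.18 × m. At p = 0.24, OR = 2.7 and ρ = 0.7 these are 0.037 and 0.026, a spurious decline of 0.011. The summary is a check on composition, not a replacement estimate.

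**The case against.** - **Direction and size are assumed.** This stands. A reader might infer that the reported month-12 gain will be overstated. The documents do not support that: they give no dropout rate and nothing to show that poor responders stay away. Section 6.5 provides unscheduled visits for subjects with possible recurrence, who may stay in closer contact than others.
- **A repeated-measures model is no cure.** This stands. A reader might infer that the model avoids the problem altogether. Step 2 gives zero error because missingness there depends on a recorded score; Step 3 shows what remains when it does not.
- **Subjects with no follow-up score.** Section 5.5 defines loss to follow-up as two consecutive missed time points, and section 6.4.1 schedules only two follow-up visits. On the natural reading, a subject lost in this way has a baseline score only. A model of change scores that requires a follow-up value would drop exactly these subjects. This stands, and is why baseline belongs in the response vector. Even then the baseline score is all the information they add.
- **The two means are not from separate groups.** This stands. With month 6 complete and 11-24% missing at month 12, 76-89% of subjects are in both means. The visible plan also makes no formal comparison of the two visits.
- **The plan already reports numbers of observations, and redacted text may say more.** Counts would reveal uneven attendance but would not adjust for it. Section 8.0 permits additional analysis without specifying any. The redactions limit the point to the visible text.
- **Low stakes.** This stands. Quality of life is an additional evaluation in a single-arm descriptive study with no pass/fail criteria (section 8.10).

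**Conclusion.** The point holds as a modest, conditional weakness. The visible plan reports EQ-5D-5L change by visit in whoever has data, without imputation. The two means can therefore differ in composition, and the month-12 mean leaves relevant month-6 information unused.

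Under the stated assumptions, the month-12 mean is about 0.005-0.026 too high if missingness follows the month-6 response, and unbiased if data are missing completely at random. A likelihood-based repeated-measures estimate removes that error when missingness depends on observed scores. When missingness follows the unrecorded month-12 score, it leaves about half to three quarters of a larger error.

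Every magnitude rests on assumed inputs. What is affected is the reading of the quality-of-life means and of any nominal p-value attached to them, not a success decision.

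**What to change.** In section 8.2.1:

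1. Keep the observed n, mean and SD of EQ-5D-5L change at each visit, and name the score being analysed, since the visible text does not define one.
2. Add a likelihood-based repeated-measures estimate of mean change at months 6 and 12. Use baseline, month 6 and month 12 scores as the response vector, visit as factor and an unstructured covariance, so that subjects with only a baseline score are retained.
3. Show the observed month-6 and month-12 change in subjects with both visits, labelled as a check on composition.
4. State that the model removes attendance bias only if missingness depends on observed scores, and only reduces it otherwise.

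The cost is a few sentences of plan text and one standard SAS procedure, with no new data. Nothing is imputed, so the rule in section 8.7, "Missing data will not be imputed", is respected. The downside is one extra model resting on a missing-at-random assumption that the data cannot verify. If the split in section 8.5 applies, it must be fitted separately in paroxysmal and persistent AF.
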